### 3 INVESTIGATIONAL PLAN

#### 3.1. Overall study design

This is an open-label, 12-month pilot study of Pasireotide LAR therapy of 10 patients with silent corticotroph pituitary tumors.

Pasireotide LAR 40 mg will be administered monthly. Baseline and monthly visits on therapy will monitor plasma levels of POMC, other pituitary function, safety labs, glucose tolerance, physical examination, and visual fields. Pituitary MRI will be done at baseline, 6 months and 12 months of therapy.

The starting dose is Pasireotide LAR 40 mg/month IM, this will be increased to 60 mg/month at 6 months if a fall in POMC levels and/or tumor shrinkage are not attained. LAR will be administered monthly with the last injection at Week 44.

#### 3.2 Study population

Ten (10) patients with clinically nonfunctioning pituitary tumors of the silent corticotroph tumor subtype will be studied in this protocol. Males and females are eligible for enrollment. Subjects ages 18 – 80 are eligible for enrollment. Patients will be drawn from primarily from our cohort of 285 patients with clinically nonfunctioning pituitary tumors followed in our prospective study. Patients will also be recruited from subjects treated at our Neuroendocrine Unit and Pituitary Center for who are known to have silent corticotroph pituitary tumors. The investigator will ensure that only patients who meet all

the following inclusion and none of the exclusion criteria are offered treatment in the study. The investigator will maintain an enrollment log of screened/enrolled subjects.

### **3.2.1 Inclusion and exclusion criteria**

#### **Inclusion criteria:**

Subjects must meet all of the following inclusion criteria to be eligible for enrollment into the study:

1. Adults (males and females) (ages 18- 80 years) with a diagnosis of a clinically nonfunctioning pituitary tumor of the silent corticotroph tumor type (i.e. positive ACTH staining on immunohistochemical staining of the pituitary tumor obtained at surgery)
2. Plasma POMC level within or greater than the upper limit of normal
3. Prior pituitary tumor surgery with residual or recurrent pituitary tumor visible on MRI scan that is  $\geq 5$  mm from the optic chiasm.
4. Surgical resection of the pituitary adenoma must have occurred two or more months prior to baseline visit.
5. If patients have undergone pituitary radiotherapy they must have completed their course of radiotherapy at least 2 months prior to study screening
6. No prior somatostatin analog therapy
7. No concurrent use of dopamine agonist therapy
8. No active malignancy
9. Stable pituitary hormone supplements (x 2 months) prior to baseline visit
10. Sign and date an informed consent document indicating that the subject has been informed of and agrees to all pertinent aspects of the trial

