## PROTOCOL SUMMARY

**Protocol number:** CSOM230GUS44T

**Title** PILOT STUDY OF PASIREOTIDE LAR TREATMENT OF SILENT CORTICOTROPH PITUITARY TUMORS AND EFFECTS ON PLASMA LEVELS OF POMC

**Clinical Phase:** Phase II

**Investigation Type:** Drug

**Study Type:** Interventional

**Purpose and Rationale:** The purpose of this trial is to test the main hypotheses that Pasireotide LAR treatment of patients with silent corticotroph pituitary tumors and elevated or normal plasma POMC levels will reduce plasma POMC levels and this will be associated with a reduction in pituitary tumor size.

**Primary Objective:** To determine the efficacy of Pasireotide LAR to suppress plasma levels of POMC in patients with silent corticotroph pituitary tumors.

**Secondary Objectives:** To determine the effect of Pasireotide LAR therapy on pituitary tumor volume in patients with silent corticotroph pituitary tumors.

**Study design:** This is an open-label, 12-month pilot study of Pasireotide LAR therapy of 10 patients with silent corticotroph pituitary tumors. Pasireotide LAR 40 mg will be administered monthly. Baseline and monthly visits on therapy will monitor plasma levels of POMC, other pituitary function, safety labs, glucose tolerance, physical examination, and visual fields. Pituitary MRI will be done at baseline, 6 months and 12 months of therapy. The starting dose is Pasireotide LAR 40 mg/month given as intramuscular injection. The dose will be increased to 60 mg/month at 6 months if a fall in POMC levels and/or tumor shrinkage are not attained. LAR will be administered monthly with the last injection at Week 44.

**Study Population:** The eligible patient population will consist of adult patients with known silent corticotroph pituitary tumors and elevated or normal plasma levels of POMC.

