#### 1.2.1.1 Clinical Experience

##### 1.2.1.1.1 Pasireotide LAR

Pasireotide LAR has been extensively investigated in the clinical development program for healthy volunteers and various patient populations. Completed studies and studies with completed interim analyses are shown in the INVESTIGATOR'S BROCHURE, V15, P. 44, Table 5-1.

Pasireotide LAR demonstrated favorable PK profile for extended release in healthy volunteers and patients. PK steady state was achieved following 3 monthly (q28d) intra-muscular (i.m.) injections of pasireotide LAR in a study with both acromegaly and carcinoid patients. PK exposures of trough concentrations were approximately dose-proportional. CL/F of the Pasireotide LAR formulation was comparable to CL/F of the s.c. formulation (4.3-9.0 L/h). T1/2 for the Pasireotide LAR formulation was approximately 16 days, suitable for monthly dosing. The relative bioavailability of the Pasireotide LAR formulation to the s.c. formulation was complete, ranging from 106% to 148%. PK exposures in acromegaly patients were comparable to those in healthy volunteers. PK exposures in carcinoid patients were 2-fold higher than in healthy volunteers.

The efficacy of pasireotide LAR in acromegaly patients is based on CSOM230C2305, the phase III study to assess the safety and efficacy of pasireotide LAR vs octreotide LAR in patients with active acromegaly. In this study, pasireotide LAR was shown to be significantly superior to octreotide LAR for the treatment of acromegaly in medically naïve patients in terms of biochemical control (GH < 2.5 µg/L and normalization of IGF-1 levels) (31.3% vs. 19.2%; p-value 0.007), providing higher response rate in both de novo patients and in patients with prior pituitary surgery (25.7% vs. 17.3% in de novo patients; 39.4% vs. 21.8% in postsurgical patients). Pasireotide LAR was as effective as octreotide LAR in reducing tumor volume, improving acromegaly symptoms and ring size, and quality of life (27).

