In our ongoing "Prospective Study of Clinically Nonfunctioning Pituitary tumors" funded by the NIH (DK073040), we are prospectively studying a large cohort (currently 285) of patients who have presented with apparent clinically nonfunctioning pituitary tumors. One AIM of this study has been to identify silent corticotroph pituitary tumors based on measurement of plasma POMC levels. All patients have been screened with POMC measurements and POMC levels have been followed over time in patients who had elevated levels, in many also after surgical removal of the pituitary tumor. A number of patients in this cohort have been identified with levels of POMC above our normal range. Those patients with elevated plasma POMC levels were found to have pituitary tumors positive for ACTH on immunohistochemical analysis. We have also examined another group of patients with known silent corticotroph pituitary tumors and some of these patients have been found to have elevated plasma POMC levels. We hypothesize based on the rationale described above that these patients with clinically silent corticotroph pituitary tumors (ACTH positive on pathology) and elevated POMC levels in plasma will respond to pasireotide therapy. Detection of a lowering of the increased plasma levels of POMC by pasireotide would show that POMC measurement is a clinically relevant marker to follow during pasireotide treatment of silent corticotroph tumors. POMC levels could also

serve as a marker that identifies patients in whom pasireotide would be more likely to be effective. Although we do not have evidence yet that pasireotide will produce shrinkage of silent corticotroph tumors, POMC lowering may be associated with tumor shrinkage since somatostatin analog therapy typically produces tumor shrinkage when the biomarker of the tumor is suppressed reflecting tumor cell suppression. This will be tested in this study by examining tumor size changes along that of POMC levels in patients with silent corticotroph tumors.

Thus, our preliminary results suggest that plasma POMC levels will be a useful marker for silent corticotroph pituitary tumors. In this project, we will examine the use of plasma POMC level as a marker for the effectiveness of medical treatment of silent corticotroph tumors with Pasireotide.

[figure not shown]

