### 3.3. Treatment

#### 3.3.1. Investigational Therapy

Patients who have provided written informed consent will undergo screening procedures. Once eligibility is established patients will begin therapy with Pasireotide LAR 40 mg.

Pasireotide LAR 40 mg will be administered as intra-muscular (i.m.) intragluteal injections every 4 weeks. Uptitration will occur to Pasireotide LAR 60 mg after 6 months of therapy with Pasireotide LAR 40 mg if POMC level has not been suppressed and/or pituitary tumor shrinkage has not occurred. For patient receiving 40 mg dose down-titration to 20 mg is permitted for patients who do not tolerate 40 mg. For patients who are up-titrated to the 60 mg dose down-titration to 40 mg is permitted if tolerability issues occur on this higher dose.

Medication labels will comply with legal requirements and be printed in English. The storage conditions for study drug will be described on the medication label.

Should anti-diabetic treatment be needed during the study (see adverse events) this will be provided by the investigator according to standard clinical practice for diabetes care. The order of initiation of anti-diabetic therapy is expected to be, but is not prescribed as part of this protocol:

- Metformin at individual doses starting from 1000 mg/day to maximum dose according to the approved package insert and depending on the patient tolerability
- Sitagliptin 50 or 100 mg administered orally once a day

- Insulin administered s.c. according to package insert

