## 4 Statistical methods

### 4.1. Efficacy assessments

Specific Study Endpoints:

1. Percentage of patients with suppression of POMC level.
2. Percent change from Baseline of POMC level at each visit.
3. Percent change from Baseline of POMC level at final visit.
4. Percent change from baseline in pituitary tumor volume.
5. Change from baseline of fasting insulin or glucose levels or insulin sensitivity indices.
6. Change in HbA1C level

The primary outcome will be differences in POMC from baseline to 12 months after Pasireotide LAR therapy. We will also assess differences in POMC/ACTH ratios from pre to post-treatment. Changes in pituitary tumor size from pre to post-pasireotide therapy will be assessed. Patient characteristics will be summarized by descriptive statistics. Frequencies and percentages for categorical variables and mean, standard deviation, median, minimum and maximum for continuous variables. The paired t-test and Wilcoxon signed test will be used to evaluate the change in POMC level from baseline to final study visit as appropriate. Peptide levels and ratios will be compared by nonparametric approach. Repeated measures ANOVA will also be used to analyze the change in POMC levels over time during pasireotide therapy. Statistical Analysis will be performed by SAS 9.3.

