## 4.2 Sample size and power considerations

Sample size and power calculation was carried out for percentage change in POMC level from baseline to final study visit based on prior data examining percentage changes in plasma ACTH from before to after Pasireotide treatment in patients with Cushing's disease. In two Cushing's disease studies, percentage lowering of ACTH level was on average 20% with a 15% SD in this change (31,32). This change was clinically significant, it was associated with 100% of subjects having at least 25% reduction in pituitary tumor size and significant reductions in mean 24 urine free cortisol levels (31,32). From these data, we also expect POMC levels to be reduced by 20% with Pasireotide LAR therapy of POMC secreting silent corticotroph tumors. If the true difference from baseline to post-Pasireotide LAR therapy represents a 20% fall in POMC level and SD of this difference is 15% we will be able to reject the null hypothesis that the percentage change in POMC level is 0 with power >90% and 10 pairs of Pasireotide LAR treated patients with a significance level 0.05 using a two-sided paired t-test.

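### Does admitting patients with normal POMC leave the suppression endpoint without a usable meaning?

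*Combined protocol and SAP*

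**What the plan says.** **Who may enter.** Inclusion criterion 2 (Section 3.2.1, repeated in the Protocol Summary) reads "Plasma POMC level within or greater than the upper limit of normal". The Protocol Summary confirms that normal values are meant: its main hypothesis is that treating "patients with silent corticotroph pituitary tumors and elevated or normal plasma POMC levels will reduce plasma POMC levels". The background (Section 1.1) and rationale (Section 2.1) are narrower and speak of elevated levels.

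**The endpoint.** Section 4.1 lists six endpoints. The first is "Percentage of patients with suppression of POMC level". It gives no threshold, no reference to the normal range and no visit, and no other section defines it. Endpoints 2 and 3 are the percentage change in POMC at each visit and at the final visit.

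**Nearby wording.** The month-6 dose rule is worded two ways: "if a fall in POMC levels and/or tumor shrinkage are not attained" in Section 3.1 and "if POMC level has not been suppressed and/or pituitary tumor shrinkage has not occurred" in Section 3.3.1. Section 2.1 says "Detection of a lowering of the increased plasma levels of POMC by pasireotide would show that POMC measurement is a clinically relevant marker". Section 1.2.1.1.1 reports acromegaly results for this drug in terms that include "normalization of IGF-1 levels".

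**The primary outcome.** The objectives table (Section 2.2) pairs the aim of suppressing POMC with an endpoint of change from baseline to 12 months. Section 4.1 tests that change with a paired t-test or a Wilcoxon test. Section 4.2 bases the power on a true difference that "represents a 20% fall in POMC level and SD of this difference is 15" per cent, with 10 patients and two-sided 0.05.

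**The concern.** Endpoint 1 is a yes/no call for each patient with no rule attached, and three rules can be drawn from the text: any fall, a lowering of raised levels, or a return to normal. A patient who starts normal can never meet the second and meets the third before treatment. The first is met by chance in about half of patients when the drug does nothing.

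The trial is open-label with one arm, so no control percentage would show up a lenient rule. If the rule were chosen after the results were known, the reported percentage could be moved a long way, and each reclassified patient moves it by 10 points. Section 2.1 hopes to establish POMC as a marker of response, so a responder percentage is likely to be quoted.

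**Working it through.** **1. The plan's own figure.** Inputs from Section 4.2: mean fall 20%, SD 15%, n = 10, two-sided 0.05. Noncentrality = (20/15) × √10 = 4.22 on 9 degrees of freedom. Power = 96.2%, so the stated figure above 90% reproduces; n = 9 would still give 93.7%. Endpoint 1 does not enter this calculation.

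**2. Share counted as suppressed, by minimum fall c.** With a normal model and SD 15%, P(fall ≥ c) = Φ((m − c)/15), where m = 20 for the planned effect and 0 for an inert drug.

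| Minimum fall c | Planned effect | Inert drug |
|---|---|---|
| any (0%) | 90.9% | 50.0% |
| 10% | 74.8% | 25.2% |
| 20% | 50.0% | 9.1% |
| 25% | 36.9% | 4.8% |

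The 50% does not depend on the SD, but it needs symmetric changes, no ties and one post-baseline value. Ties at the assay floor of 7.5 fmol/ml (Section 4.1) would lower it. Counting a fall at any of 12 exchangeable post-baseline visits would raise it to 12/13 = 92.3%. The other inert-drug figures depend on the SD, which Section 4.2 takes from ACTH in treated Cushing's disease. If the SD for an inert drug were 10% to 30%, a fall of at least 20% would occur in Φ(−20/10) = 2% to Φ(−20/30) = 25%.

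**3. Does normal baseline POMC matter?** Percentage change is 100 × (final − baseline)/baseline. The upper limit of normal (ULN) is not in the formula, so every row of the table holds equally for normal and elevated baselines. Inclusion 2 does not produce the 50%.

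**4. The readings where it would matter.** Assume, for illustration, 3 normal patients and 7 at 1.5 × ULN; neither figure is in the documents.
- Lowering of raised levels: 0.7 × 90.9% = 63.6% for the planned effect and 0.7 × 50.0% = 35.0% for an inert drug.
- Return to normal: each of the 7 needs a fall of 1 − 1/1.5 = 33.3%, with probability Φ((20 − 33.3)/15) = 18.7% or Φ(−33.3/15) = 1.3%. If the 3 normal patients stay normal, the share is (3 + 7 × 0.187)/10 = 43.1% or (3 + 7 × 0.013)/10 = 30.9%.

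The spread is wide, but neither reading is set out as a POMC endpoint. The first comes from a rationale sentence about marker value, and the second from GH and IGF-1 control in another disease.

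**5. How far ten patients separate the cases.** Under any fall at one visit, 8 or more of 10 count in 94.4% of trials with the planned effect and 5.5% with an inert drug. Five or more count in 62.3% of inert trials. The exact 95% interval for 5 of 10 is 18.7% to 81.3%.

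**6. What would stand beside a misleading 50%.** At SD 15%, the 95% half-width for the mean change is 2.262 × 15/√10 = 10.7 points. An inert drug would be expected to show a mean change near 0 ± 10.7, and the planned effect a fall of 20 ± 10.7.

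**The case for a change.** The strongest case for a change is that endpoint 1 heads the list, must differ from endpoints 2 and 3, and cannot be computed without a rule. Writing one takes a line of text and adds no patients, visits or assays. Normal-baseline patients also rule out return to normal as a convenient default, and the normal range is itself described as preliminary.

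Part of this stands. The definition is missing for every patient, the visit is missing too, and so is the handling of patients who withdraw. A rule settled after on-treatment POMC has been seen would deserve little weight.

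The rest does not carry. A fall from the patient's own baseline is usable in both groups. It is lenient at 91% against 50%, but it does separate a working drug from an inert one. That an inert drug under any fall (50%) scores above the planned effect under return to normal (43.1%) compares two different definitions and shows a fault in neither. The wording about a fall belongs to the dose rule; its link to endpoint 1 is an inference from Section 3.3.1. A better threshold would rest on assay and within-patient variability, which the documents do not give, so a revision urged from these pages would still leave the key number open.

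**Conclusion.** No change to the plan follows. This is an unwritten definition for a descriptive endpoint, a gap that analysts can fill sensibly: a fall from the patient's own baseline at the 12-month visit, of a size fixed before on-treatment POMC is examined. The objectives table in Section 2.2 already points to change from baseline. Inclusion 2 is not the cause, because the same gap exists for every patient.

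In size, an any-fall rule would read about 50% for an inert drug, given symmetric changes, no ties and one post-baseline value, against 91% for the planned effect at SD 15%. That affects how one percentage with a very wide interval should be read. It does not affect the primary outcome, its tests, the 96.2% power on the plan's stated inputs, or endpoints 2 and 3. The larger swings, such as 43.1% against 30.9%, need assumed patient mixes and readings that the plan does not state for POMC. The two wordings of the dose rule should be reconciled with each other, but that is separate from this endpoint, and nothing here bears on what the rule should be.

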
There is currently no option for medical therapy of CNFA, in general, or specifically of silent corticotroph tumors. Silent corticotroph tumors can range from being completely asymptomatic to becoming large and causing significant hypothalamic/pituitary dysfunction and visual symptoms, and most data support that this type of tumor has a more aggressive phenotype (10,18,19). Current therapy consists primarily of surgical removal of the tumor and for recurrent or residual tumors, repeated surgery and/or radiotherapy. In very aggressive tumors, chemotherapy has been tried with some success (20). Therefore, a need exists for a medical therapeutic option for the treatment of this tumor type. This project assesses this clinical need.

This protocol is a pilot study of the efficacy of Pasireotide LAR for the treatment of silent corticotroph pituitary tumors that have elevated plasma levels of POMC. We hypothesize that elevated plasma POMC levels will be a marker for this tumor type and the response of this tumor type to Pasireotide LAR therapy.

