#### POMC Precursor ELISA:

POMC precursor will be performed by ELISA with antibodies provided by [name]. For this assay capture monoclonal antibody is directed against ACTH 10-18 and detection antibody is directed against  $\gamma$ -MSH. Affinity purified human 31K POMC is used for standards. The assay has 100% crossreactivity with 22K pro-ACTH but none with ACTH,  $\alpha$ -MSH or  $\gamma$ -MSH (16,29,30). Assay sensitivity is 7.5 fmol/ml. Normal values for this POMC precursor have been preliminary established by our group (14) and a large-scale normal value study for plasma POMC levels is currently being conducted by [name]. ACTH will be measured by solid phase, two-site sequential chemiluminescent immunometric assay and cortisol by solid-phase, competitive chemiluminescent enzyme immunoassay (Immulite 1000), UFC by Liquid-Chromotography-Tandem Mass Spectrometry and Late night salivary cortisol by Mass Spectrometry. Insulin will be measured by immunofluorometric assay (DPC Immulite). Glucose will be determined by automatic hexokinase method.

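### Does the plan need a written rule for POMC results below the assay sensitivity of 7.5 fmol/ml?

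*Combined protocol and SAP*

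**What the plan says.** Eligibility (section 3.2.1, item 2, repeated in the Protocol Summary) rests on "Plasma POMC level within or greater than the upper limit of normal". The purpose statement in the Protocol Summary likewise covers both elevated and normal POMC. Background and rationale are narrower: section 1.1 speaks of "silent corticotroph pituitary tumors that have elevated plasma levels of POMC", and section 2.1 of "Detection of a lowering of the increased plasma levels of POMC by pasireotide".

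The assay text in section 4.1 states "Assay sensitivity is 7.5 fmol/ml" and "Normal values for this POMC precursor have been preliminary established by our group", citing a publication for those values. No limits are printed.

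The endpoint list in section 4.1 includes "Percentage of patients with suppression of POMC level" and "Percent change from Baseline of POMC level at final visit", plus percent change at each visit. The primary outcome is worded differently, as a change or difference in POMC from baseline to 12 months (Protocol Summary, section 2.2, section 4.1). It is tested by paired t-test or Wilcoxon signed test as appropriate. In section 4.2, "Sample size and power calculation was carried out for percentage change in POMC level from baseline to final study visit". Neither section gives a rule for a result below sensitivity.

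**The concern.** A percent change divides by the baseline. If the baseline is below 7.5 fmol/ml, the divisor is whatever number the analyst substitutes, and the patient can be scored only as unchanged, risen or missing. Such a patient cannot count as suppressed either. If only the 12-month result is below 7.5, the percent change is bounded but is not a single value.

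Patients with normal POMC are admitted, all entrants have had tumor surgery, and the drug is expected to lower POMC, so low results are plausible. With ten patients in an open-label, single-arm study, a scoring rule chosen after the data are seen could move the estimate and perhaps the significance of the main result.

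**Working it through.** **Inputs.** Sensitivity 7.5 fmol/ml (section 4.1). Mean fall 20%, SD 15%, ten pairs, two-sided 0.05 (section 4.2). The share of patients near 7.5 is not in the documents, so it can only be an assumed range.

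**1. The plan's own figure.** Noncentrality = (20/15) × √10 = 4.22 with 9 degrees of freedom. Power is 0.962, which agrees with the stated value above 90%. Leaving out one, two or three patients gives 0.937, 0.896 or 0.834.

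**2. When the limit matters.** A 20% fall stays measurable if the baseline is at least 7.5/0.8 = 9.375 fmol/ml. For a baseline of 9 and a 12-month result below 7.5, the scored fall depends on the substitute:

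| Substitute | Scored fall |
|---|---|
| 7.5 | 1 − 7.5/9 = 16.7% |
| 7.5/√2 = 5.30 | 41.1% |
| 7.5/2 = 3.75 | 58.3% |
| 0 | 100% |

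**3. One patient with baseline below 7.5.** Let nine patients have mean −20 and SD 15. Their sum of squares is 8 × 225 + 9 × 400 = 5400. Add a tenth with percent change c. The mean is (−180 + c)/10 and the variance is (5400 + c² − 10 × mean²)/9.

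| Tenth patient | c | Mean | SD | t | p |
|---|---|---|---|---|---|
| Left out | – | −20.0 | 15.0 | −4.00 | 0.004 |
| Below 7.5 at both visits, any positive substitute | 0 | −18.0 | 15.5 | −3.67 | 0.005 |
| 12-month value 9, substitute 7.5 | +20 | −16.0 | 19.0 | −2.67 | 0.026 |
| 12-month value 9, substitute 5.30 | +69.7 | −11.0 | 31.7 | −1.10 | 0.30 |
| 12-month value 9, substitute 3.75 | +140 | −4.0 | 52.5 | −0.24 | 0.82 |

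**4. How likely are the last three rows?** From a baseline just under 7.5, reaching 9 is a rise of at least 20%. With true change normal (mean −20%, SD 15%), the probability is 1 − Φ((20 + 20)/15) = 1 − Φ(2.67) = 0.4%, and it is smaller for any lower baseline. With baselines assumed uniform on 5 to 10 or on 7 to 9 fmol/ml, the combination of baseline below 7.5 and 12-month value of at least 9 occurs in about 0.02% to 0.05% of such low patients. By contrast, from a baseline just under 7.5 the 12-month value is again below 7.5 with probability Φ(20/15) = Φ(1.33) = 91%, and more for lower baselines. The second row of the table is therefore the usual case.

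**5. Several low patients (assumed).** All ten truly fall 20% (SD 15%), and k have a low baseline. Five rules are compared: set to 7.5, to 7.5/√2 or to half; drop the patient if either value is below 7.5; drop only if the baseline is, otherwise set to 7.5. The share of simulated trials in which significance differs between any two rules is:

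| Baseline range | k=1 | k=2 | k=3 | k=5 |
|---|---|---|---|---|
| 5 to 10 | 2% | 6% | 11% | 27% |
| 7 to 9 | 4% | 9% | 16% | 40% |

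If only three rules are compared (7.5, 7.5/√2, drop if baseline is below 7.5), the k=3 shares fall to about 5% and 9%.

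**6. Difference scale.** If the primary outcome is read as worded, as a difference, there is no denominator to lose. Any substitute from 0 to 7.5 moves a patient's difference by at most 7.5 fmol/ml, hence the mean of ten by at most 0.75 fmol/ml per patient.

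**The case for a change.** The case for a change is that the gap is certain from the text and closing it would take a few sentences and no new samples. Section 2.1 reports raised POMC in only some patients with known silent corticotroph tumors, so normal values will be enrolled. The Wilcoxon option does not help, since nothing is said about ties or censored values. A difference scale also needs some number for a result below 7.5. If several of ten patients sit near the limit, the choice of rule can decide significance in a noticeable share of trials.

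The omission stands, and so does the arithmetic. The reach does not. Eligibility does imply a lower bound, namely the lower limit of the normal range, which comes from a cited source and is simply not printed. If that limit is at or above 7.5, a patient reading below it at screening is ineligible, although a later baseline sample could still read lower. If it is well above 9.4, even the planned fall normally stays measurable. The assay text also does not say that readings under 7.5 go unreported as numbers. The 27% and 40% shares need half the patients in a narrow assumed band and count disagreement among five rules, when an analyst would use one and check another.

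Nor is there an obviously better rule to write in. Setting results to 7.5 is the most biased of the five for the mean: with three low patients (baseline 5 to 10) it estimates a fall of 15.5% when the truth is 20%, with power about 88%. Halving gives 19.4% there but overshoots to 22.8% when baselines lie between 7 and 9.

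**Conclusion.** No change to the plan is needed. What is missing is a data-handling convention that analysts supply as a matter of course: one constant for results below sensitivity at every visit, a count of such results, a check with another constant, and a patient unmeasurable at baseline reported as not evaluable for suppression. No stated rule produces a wrong answer, and the power statement in section 4.2 is correct (96.2%).

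Under the plan's assumptions, one patient below 7.5 at both visits moves the result from p=0.004 to p=0.005. The reversals in significance from a single low-baseline patient in the example need a rise with a probability of at most 0.4%. With one low patient, the choice among five rules changes significance in 2% to 4% of trials. The effect would be larger only if several of the ten had baselines close to 7.5, which the documents neither show nor rule out.

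The narrower wording in sections 1.1 and 2.1 is background. The purpose statement and the eligibility criterion agree with each other, and no analysis depends on the difference.

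This rests on the section 4.2 assumptions (20% fall, SD 15%, normal) and on the normal range being unknown from the documents.
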